SA#1: To test the hypothesis that BCQR will improve clinical parameters of insulin action in T1D (insulin dose, mean glucose and glycemic variability by continuous glucose monitoring [CGM], postprandial glucose excursion by glucose and insulin area under the curve during MMTT). We further hypothesize that (1) these benefits will incur due to improved postprandial suppression of glucagon and lipolysis and (2) the decrease in chronic SNS tone will lead to improved SNS responsiveness to hypoglycemia, with beneficial effects on hypoglycemia awareness and counter-regulatory response (hypoglycemia awareness questionnaire) and susceptibility to hypoglycemia (CGM).

SA#2: To investigate clinical parameters that may predict response to BCQR in order to allow targeted use of this intervention if appropriate. Subgroup analyses will be performed by age, BMI and estimated insulin sensitivity. Multivariate modeling will address other potential predictors including C-peptide, fasting NEFA, baseline HbA1c, sex, sleep characteristics, circadian rhythm delay.

SA#3: To test the hypothesis that BCQR-induced reduction in SNS activation, NEFA levels, and vascular IR will improve vascular function (arterial stiffness by Dynapulse and endothelial function by EndoPAT) and decrease blood pressure.

II. Background and Significance:

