A. Outcome Measure(s):

Primary outcome measures are mean CGM glucose and insulin dose (SA#1), impact of age and BMI on response to therapy (SA#2) and improvement in brachial artery distensibility and RH-PAT (SA#3). Insulin dose was chosen as a clinical primary outcome because of the short treatment duration and to allow insulin dose adjustments as needed to avoid hypoglycemia. Secondary outcomes (see detailed methods below) include measures of (1) glycemic control (CGM parameters (SD, %hyperglycemic)); (2) baseline/postprandial metabolic labs [area under the curve (AUC) for MMTT glucose, insulin, NEFA, triglycerides, glucagon, and glucagon-like peptide1 (GLP1); (3) hypoglycemia frequency and awareness (CGM %hypoglycemic, hypoglycemia symptoms scores (Gold method, Clarke method, and the McAuley score⁶⁴⁻⁶⁷); (4) SNS activity (heart rate variability); (5) other metabolic markers (HDL, LDL); (6) circadian rhythm/sleep effects (sleep quality scores, measured sleep with actiwatch sleep monitor); (7) CVD measures (arterial stiffness by Dynapulse, endothelial function by EndoPAT, and blood pressure), and (8), blood storage for future inflammatory (IL-6, TNF- α , hsCRP, adiponectin), and vascular (endothelin 1, PAI-1, ICAM, renin, angiotensin, aldosterone) markers.

B. Description of Population to be Enrolled:

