Study population: Initially our goal is to enroll 60 T1D subjects (50% male) with the goal of completing 40 in the adult cohort. Ultimately, if the study drug is tolerated and safe in our adult cohort, we plan to amend the protocol to include adolescents, with involvement of [name], the co-PI on the JDRF award. With the addition of the adolescent cohort, we plan to recruit 133 T1D subjects with the goal of completing 80. Submission of this amendment will occur in late year 1 ONLY IF there is no concerning safety signal in the adult cohort. Inclusion criteria: (1) T1D of >9 months duration based on a clinical course consistent with T1D and rapid conversion to insulin requirement after diagnosis (2) HbA1c 6.5-10% (adults) or any HbA1c up to 12% (pediatrics) and (3) age 12-60 years of age. Exclusion criteria include (1) any comorbid condition associated with inflammation, IR, or dyslipidemia including cancer (with the exception of skin cancer), heart failure, active or end stage liver disease, end stage kidney disease, inadequately treated thyroid disease, or rheumatologic disease; (2) tobacco or marijuana use; (3) pregnancy; (4) regular or frequent oral steroid use; (5) current use of insulin sensitizing medications, neuroleptics or ergot-related medications, or triptan medications for migraine, (6) diagnosis or history of psychosis and (7) diabetes of other cause such as MODY or cystic fibrosis-related diabetes. BMI will not be restricted in order to allow secondary analysis for effects of BMI on responsiveness to BCQR. Postmenarchal premenopausal females will be tested in the early follicular phase (cycle d2-10) where possible.

C. Study Design and Research Methods

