Recruitment: Ultimately 133 T1D subjects (50% male, 50% adolescent) will be enrolled with the goal of having 100 eligible and completing 80 (see power analysis). Recruitment will begin year 1 for the adult cohort and an adolescent cohort will be added in year 2. We will begin with a mass mailing to the established CACTI cohort of >600 adults with T1D mailing list established through [name] clinical relationship. In addition, a co-investigator from the Barbara Davis Center adult T1D clinic ([name]) is included specifically for recruitment purposes. Through these approaches we hope to have the full adult cohort recruited, but not completed, by the end of year 1. Late in year 1, any adverse events will be thoroughly reviewed by the safety officer to assess for any safety concerns (in particular hypoglycemia) prior to submitting an amendment to broaden the age range to add the adolescent cohort. However, we do not expect to encounter significant safety issues since higher doses and much longer durations of standard release bromocriptine are widely used in adults and children for other medical conditions. Beginning year 2, adolescent recruitment will consist of patients from the Barbara Davis Center for Childhood Diabetes (BDC) where co-investigator [name] is a medical provider and has a weekly clinic. [name] has excelled when recruiting adolescent T1D patients as she currently recruits for multiple protocols researching the abnormalities associated with T1D. Furthermore, [name] holds a weekly Endocrine Clinic and is a provider in the Lifestyle Medicine Clinic at the Children's Hospital of Colorado where she has a clinical relationship with many patients with T1D and other endocrine disorders. Co-investigator [name] is also a physician at the BDC and holds multiple weekly clinics with T1D patients. IRB approved flyers will be placed in private Endocrine clinics in the Denver Metro area. Through these approaches we hope to have the full adolescent cohort recruited. We include both lean and obese participants as BMI and age-based differences in IR, glycemic control, hormone levels, sleep patterns and diabetes duration may impact response to BCQR. This recruitment strategy has been used successfully for our similarly powered individual ongoing studies.

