Power and Sample Size: Power analysis and sample size are based on expected changes from the literature and from preliminary data for the primary outcomes for each aim. The sample size for the entire study was based on the power analysis for the subgroup analyses by age, in order to ensure adequate power to detect clinically meaningful treatment effects within each subgroup. In addition, we plan to examine the results by other characteristics (e.g. by obesity level, positive c-peptide status, etc.) in exploratory analyses which are not fully powered, but which may provide insight into heterogeneity in response to the therapy, thus guiding a future clinical trial if results of this study are positive. Desired α is set at 0.05. Since data used for this analysis are from within-subjects comparisons, repeated measures analysis will be used to compare outcome variables after each treatment (placebo, BCQR), adjusting for the randomization assignment of treatment order.

Assessment of Efficacy

The primary efficacy parameters will be change in insulin dose and CGM mean glucose on treatment versus placebo. Secondary efficacy measures will include change in post-MMT glucose and insulin AUC, and change in other CGM parameters (SD, %hyperglycemic, % hypoglycemic). Total daily basal and bolus insulin dose will be obtained at screening, and then at time zero for each medication phase. Insulin diaries will be obtained during the last week of each phase. Change in total, basal, and bolus insulin dose in units per day and total insulin in units per kg per day will be examined between medication phases to determine whether insulin requirements were lower at the end of the BCQR phase than the end of the placebo phase. Similarly, change in mean CGM glucose from the last 2 weeks of each medication phase will be examined to determine if overall mean glucose is decreased while on treatment versus placebo.

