Analysis Plan: All randomized subjects will be included in the analysis using an intention to treat analysis. The change in insulin dose, CGM-glucose and other metabolic parameters will be compared between the placebo and treatment visits in each subject using paired t-tests for univariate comparisons, and using repeated measures linear regression to adjust for covariates including age, diabetes duration, baseline HbA1c, and BMI. An interaction term will be entered into the model to examine whether the effect of treatment on either outcome differs among adults linearly by age, and if there is a significant interaction ($p<0.10$), results will be stratified by age group. We will also use interaction terms to assess whether the effect of treatment differs by BMI. We will also examine whether diabetes duration and initial HbA1c have an effect on outcomes by testing for an interaction between these continuous variables and the change in insulin dose and CGM-glucose. Change in vascular parameters will also be examined using paired t-test and repeated measures regression to determine if the treatment with BCQR affects vascular stiffness or function.

SA1: Effect on metabolic parameters (insulin dose, mean glucose and glycemic variability by CGM, postprandial glucose AUC by MMTT): While there are no published data on the effect of BCQR on insulin dose, prior data on the effect of Metformin⁸⁸ indicate that the change in daily insulin dose is normally distributed with standard error of 2.2 units (SD 7.6) and data from prior studies in adults with T1D performed at our center indicate that the change in total daily insulin dose

over 4 weeks is normally distributed with a standard deviation of 15 – 18.8 units/day. Assuming a SD of 18.8 to be conservative, we will be able to detect a true change in the daily insulin dose of matched pairs of \pm 5.9 units/day with 80% power in the overall group (n=80) and a change of 8.3 units/day within each age group (n=40). In a prior study of the efficacy of BCQR in adult patients with T2D, study participants treated with BCQR experienced a decrease in fasting plasma glucose level of 36.09 mg/dl and a decrease in post-prandial plasma glucose of 14.38 mg/dl after 12 weeks of treatment⁸⁹. In the overall study group, we will be able to detect a change in CGM-glucose of 3.1 mg/dl with 80% power in the entire study group and a change in CGM-glucose of \pm 4.4 mg/dl in each age group, assuming an SD of 10.03 mg/dl.

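### The age-interaction test is confined to adults yet decides whether results are split by age group, so it cannot directly test the adolescent-adult difference behind the sample size

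*Combined protocol and SAP*

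**What the plan says.** All references are to the combined protocol and SAP.

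- **Section F, Analysis Plan.** An interaction term examines whether the treatment effect "differs among adults linearly by age, and if there is a significant interaction", with significance set at p<0.10. If it is significant, "results will be stratified by age group". The interactions with BMI, diabetes duration and baseline HbA1c carry neither an adult restriction nor a gate.
- **Specific Aims, SA#2.** "Subgroup analyses will be performed by age, BMI and estimated insulin sensitivity". No condition is attached.
- **Section IV.A, Outcome Measure(s).** The impact of age (with BMI) on response is the primary outcome for SA#2.
- **Section IV.B, population.** Eligibility is "age 12-60 years of age".
- **Section IV.C, Recruitment.** "Ultimately 133 T1D subjects (50% male, 50% adolescent) will be enrolled".
- **Section F, Power and Sample Size.** The whole study was sized on the subgroup analyses by age, "in order to ensure adequate power to detect clinically meaningful treatment effects within each subgroup".
- **Section F, SA1.** Detectable within-group changes are given for each age group at n=40: 8.3 units/day and 4.4 mg/dl.
- **Section F, SA2.** A two-sample comparison of change by group is powered at 80% for 11.9 units/day and 6.4 mg/dl. Continuous age is evaluated in the overall group.
- **Section F, SA3.** The age subgroups are named as adolescents and adults.

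**The concern.** The Analysis Plan holds the only stated age-interaction rule, and it uses one contrast (a slope across adult ages) to decide whether to show another (adolescents against adults). Such a gate responds to an adolescent-adult difference only so far as that difference continues as a trend within adults. If adolescents respond differently but adults of all ages respond alike, the gate opens only at its false-positive rate.

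Two things are at stake. First, an analyst following the Analysis Plan and one following SA#2 and the SA2 power text would run different age tests on different subjects for a primary outcome, and could disagree on whether separate adolescent and adult effects are reported at all. Second, the rule can withhold the within-age-group results for which 80 completers were planned.

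**Working it through.** **1. Which comparison is powered.** Inputs from Section F: SD of change 18.8 units/day (insulin dose) and 10.03 mg/dl (CGM glucose), 40 per age group, alpha 0.05 (taken as two-sided), 80% power.

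Two-sample t-test: noncentrality = gap / (SD × √(2/40)), with 78 degrees of freedom.

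- Insulin: 11.9 / (18.8 × 0.2236) = 2.83; power 79.8%.
- CGM: 6.4 / (10.03 × 0.2236) = 2.85; power 80.5%.

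Solving for the detectable gap at exactly 80% power gives 11.92 units/day and 6.36 mg/dl, so the SA2 figures reproduce as a comparison of two groups of 40. The SA2 sentence says only that the comparison is by group. That it means the age groups follows from the n=40 per age group in SA1 and from the statement that age subgroups set the sample size.

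The SA1 figures also reproduce, by the normal approximation (1.960 + 0.842) × SD / √40: 8.33 units/day and 4.44 mg/dl.

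**2. How often the written gate opens.** The documents give no age distribution or age pattern, so these are assumptions: 40 adolescents uniform over 12-18, 40 adults uniform over 18-60, a true gap equal to the SA2 figure, one outcome at a time, no covariates.

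For the adults-only slope, noncentrality = slope × SD(age) × √40 / SD, with 38 degrees of freedom and critical value 1.686 at two-sided 0.10. Mean ages are 15 and 39, 24 years apart. SD(age) in adults is 42/√12 = 12.12. The standard error of the insulin slope is 18.8 / (12.12 × 6.325) = 0.245.

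- Flat within adults: slope 0; the gate opens at alpha, 10%.
- Half step at 18, half linear: slope 5.95/24 = 0.248; noncentrality 1.01; about 26%.
- Fully linear over 12-60: slope 11.9/24 = 0.496; noncentrality 2.02; about 63%.

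Simulation with random ages (40,000 trials per scenario), all tests at p<0.10:

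| Outcome and age pattern | Adults-only slope (as written) | Adolescent vs adult | Linear age, all 80 |
|---|---|---|---|
| Insulin, flat in adults | 10.1% | 87.6% | 72.9% |
| Insulin, half step, half linear | 26.0% | 87.4% | 88.7% |
| Insulin, linear | 62.3% | 86.1% | 96.1% |
| Insulin, no difference | 9.8% | 10.3% | 10.2% |
| CGM, flat in adults | 10.1% | 88.3% | 73.7% |
| CGM, half step, half linear | 25.8% | 87.5% | 88.8% |
| CGM, linear | 62.6% | 86.9% | 96.5% |

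**3. Sensitivity to the adult age range.** In the linear insulin case, the gate opens in 57.2% of trials with adults uniform over 18-45 and in 41.6% with adults uniform over 25-60.

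The no-difference row shows that all three tests hold their 10% level. The written gate therefore loses sensitivity without gaining protection against false positives.

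**The case against.** The strongest reply is that the texts can be read together. In a crossover, comparing within-subject change between two groups is itself the treatment-by-group interaction test. SA2 in Section F describes such a comparison, and continuous age in the overall group. The Analysis Plan sentence could then be an extra check for a trend across the wide adult range, or wording left from the stage when only adults were to be enrolled. It could also describe a model on all subjects with an age slope for adults. Finally, splitting results only after an interaction at p<0.10 is a conventional guard against over-reading subgroups.

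Part of this stands. SA2 does show that an adolescent-inclusive comparison was intended. Adolescents are left out of the age-interaction test only, not out of the main analysis, although age as a covariate does not test whether the effect changes with age. The SA#2 aim is one line and might not be expected to repeat a condition. The percentages depend on assumed age patterns, and the 10% is the worst case by construction.

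The rest does not remove the problem. The SA2 text is a power statement and does not override a stated analysis rule. Reading age group as strata within adults needs strata the plan never defines, and on that reading there is no rule for adolescents against adults. An adult-only slope in a model of all subjects still takes no information on age from adolescents. Staged enrolment may explain the wording, but Section F plans 133 enrolled, 80 completing and two age groups of 40. A conventional gate would at least test the contrast it controls. The rule mentions either outcome; even if one significant outcome opened the gate for both, the flat case could not exceed 10% + 10% = 20%.

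**Conclusion.** The concern holds and should be fixed. As written, a test among adults decides whether adolescent and adult results are separated, and it conflicts with the ungated, all-subject treatment of age elsewhere in the plan. Under the assumptions in the working, with a true gap equal to the SA2 figure, the gate opens in 10% to 62% of trials for insulin dose (10% to 63% for CGM glucose). A direct age-group term is significant in 86-88% for insulin dose and 87-88% for CGM glucose. The exact loss depends on an unknown age pattern, but the written gate does worse in every pattern examined. The overall BCQR-placebo comparison is not affected; the SA#2 age analysis is.

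**What to change.** In Section F, Analysis Plan:

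1. Replace the adults-only term with a treatment-by-age-group interaction (adolescent versus adult) fitted in all subjects, and define the two groups there.
2. State that the treatment effect and its confidence interval will be reported in adolescents and in adults whatever the interaction p-value. This follows from sizing the study on effects within each age group.
3. Keep continuous age as an additional analysis in the overall group, as SA2 already states. If a trend within adults is also wanted, label it as a separate analysis that gates nothing.

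The cost is a change of SAP wording, with no new data and no extra subjects.

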SA2: Effect in sub-groups: For comparisons of change in insulin dose and CGM-glucose by group in two-sample independent comparisons assuming equal variance and using estimates of SD as in SA1, we will have 80% power to detect a difference in the effect of BCQR treatment on daily insulin dose of \pm 11.9 units/day, and a difference in change in CGM-glucose of \pm 6.4 mg/dl. For evaluation of BMI and age as continuous variables, we will have 90% power to detect a correlation coefficient of 0.307 or greater in the overall group in univariate analysis, and a slope of 0.32 for daily insulin dose or 0.37 for BMI in linear regression analysis.

SA3: Effect on vascular measures: Change in measures of vascular health (BrachD and RH-PAT RHI as primary outcomes, AI and HRV as secondary outcomes) will be compared following placebo and treatment with BCQR. In a prior study of BrachD in healthy adolescents and young adults, BrachD was normally distributed with a SD ranging from 1.04 to 1.29. We will have 80% power to detect a difference in BrachD of 0.343 mmHg⁻¹ in the entire study group, and a difference of 0.60 mmHg⁻¹ in each age group⁵⁵. A prior study in children with T1D found an intrapatient standard deviation of 0.261 for RH-PAT RHI. Assuming this intrapatient standard deviation, in the overall group we will have 80% power to detect a change in RH-PAT RHI of 0.10% between treatment and placebo visits, and 0.10% in each age subgroup (adolescents and adults).

G. Summarize Knowledge to be Gained: BCQR has shown promise in type 2 diabetes as an oral antglycemic agent that is generally well tolerated and safe and has a novel mechanism with the potential to have significant independent benefit for vascular complications. Studies so far have shown a dramatic decrease in cardiovascular events in type 2 diabetes. The mechanism and our current understanding of T1D suggest that BCQR may also benefit individuals with T1D in terms of glycemic control, insulin resistance, and vascular complication risk. This study will provide preliminary data supporting or refuting the hypothesis that BCQR is a novel oral agent that will benefit glycemic control, vascular function and stiffness, and hypoglycemia awareness in T1D.

H. References:

1. DeFronzo RA. Bromocriptine: a sympatholytic, d2-dopamine agonist for the treatment of type 2 diabetes. *Diabetes Care*. Apr 2011;34(4):789-794.

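### SA2 claims 90% power to detect a correlation of 0.307, but with 80 subjects and two-sided alpha 0.05 the power is about 80%

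*Combined protocol and SAP*

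**What the plan says.** The Outcome Measures section lists "impact of age and BMI on response to therapy (SA#2") among the primary outcomes. Section F, SA2, gives the power for that question in two forms. For comparisons between two groups it gives detectable differences of 11.9 units/day and 6.4 mg/dl at 80% power. For age and BMI as continuous variables it says "we will have 90% power to detect a correlation coefficient of 0.307 or greater in the overall group in univariate analysis", and then adds "a slope of 0.32 for daily insulin dose or 0.37 for BMI in linear regression analysis".

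The inputs are stated nearby. The SA1 paragraph identifies the group: "with 80% power in the overall group (n=80"). Power and Sample Size sets alpha at 0.05 without giving sidedness. It also says "The sample size for the entire study was based on the power analysis for the subgroup analyses by age", so the correlation figure did not set the study size.

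**The concern.** In SA1 to SA3, every other detectable effect that comes with a stated power is given at 80%; this sentence alone says 90%. A detectable correlation depends only on n, alpha and power, so the claim can be checked without any outside SD.

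Age and BMI as modifiers of response form the SA2 primary question, and this is the only power statement for them as continuous variables. If the power is overstated, a null age or BMI result will look more conclusive than it is, and the plan intends its findings on heterogeneity of response to guide a later trial.

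The slopes in the same sentence raise a further problem. One is labelled by an outcome (insulin dose) and the other by a predictor (BMI), and no predictor SD is given.

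**Working it through.** **Inputs.** r = 0.307 and stated power 90% (SA2); n = 80 (SA1); alpha 0.05 (Power and Sample Size). Sidedness is inferred in step 1.

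**1. Reproduce the neighbouring figures to fix the convention.** SA1, paired comparison, normal approximation: detectable difference = SD × (z for alpha + z for power) / √n.

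| SD, n | Stated | Two-sided 0.05, 80% | One-sided 0.05, 80% | Two-sided 0.05, 90% |
|---|---|---|---|---|
| 18.8, 80 | 5.9 | 5.89 | 5.23 | 6.81 |
| 18.8, 40 | 8.3 | 8.33 | 7.39 | 9.64 |
| 10.03, 80 | 3.1 | 3.14 | 2.79 | 3.63 |
| 10.03, 40 | 4.4 | 4.44 | 3.94 | 5.14 |

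Only two-sided 0.05 with 80% power matches. The SA2 group comparisons (two-sample t, 40 per group, two-sided 0.05, 80% power) give 11.92 and 6.36 against the stated 11.9 and 6.4. These two checks use different formulas (normal for SA1, t for SA2) but agree on sidedness and power.

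**2. Power at r = 0.307, n = 80, two-sided 0.05.**

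- Fisher z: atanh(0.307) × √(80 − 3) = 0.3172 × 8.775 = 2.784; power = Φ(2.784 − 1.960) = Φ(0.824) = 79.5%.
- Fisher z with the bias term r / [2(n − 1)] = 0.307/158 = 0.0019: (0.3172 + 0.0019) × 8.775 = 2.801; power = Φ(0.841) = 80.0%.
- Simulated bivariate-normal data: 80.0%.
- Regression with fixed predictor: noncentrality = 0.307/√(1 − 0.307²) × √80 = 2.885, t on 78 df; power = 81.3%.

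**3. Correlation detectable at n = 80, two-sided 0.05.** Fisher z: r = tanh[(1.960 + z for power)/√77].

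| Power | Fisher z | Bias-corrected | Fixed predictor |
|---|---|---|---|
| 80% | tanh(2.802/8.775) = 0.309 | 0.307 | 0.302 |
| 90% | tanh(3.242/8.775) = 0.353 | 0.352 | 0.344 |

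The bias-corrected formula at 80% power returns the printed 0.307 to three decimals.

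**4. Other readings the plan might allow, at r = 0.307.** The Recruitment section expects 100 eligible subjects ("with the goal of having 100 eligible and completing 80") and 133 enrolled. The Analysis Plan uses p < 0.10 for an interaction.

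| n | Alpha | Power (Fisher z / simulation / fixed predictor) |
|---|---|---|
| 80 | two-sided 0.10, or one-sided 0.05 | 87.3% / 87.6–87.7% / 88.8% |
| 100 | two-sided 0.05 | 87.8% / 88.1–88.2% / 89.1% |
| 100 | two-sided 0.10, or one-sided 0.05 | 93.1% / 93.3% / 94.0% |
| 133 | two-sided 0.05 | 95.1% / 95.2% / 95.8% |

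None gives 90%. At two-sided 0.05, 90% power for r = 0.307 needs about 103 (fixed predictor) to 108 subjects (Fisher z: (3.242/0.3172)² + 3 = 107.4). Neither number is in the plan.

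**The case against.** Sidedness is nowhere stated, and the intention-to-treat wording could suggest more than 80 subjects in the analysis. With 100 subjects the fixed-predictor calculation reaches 89.1%, and one-sided 0.05 at n = 80 reaches up to 88.8%. Under those readings the gap is one to three points rather than ten. This limits certainty about its size but does not rescue the statement. SA1 puts the overall group at 80, the neighbouring figures are two-sided, and no reading returns 0.307 at 90%. The p < 0.10 rule was also written for a narrower purpose: to "examine whether the effect of treatment on either outcome differs among adults linearly by age".

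The slopes could be a separate matter. If predictor and residual SDs are both set to 1 (an assumption, not in the plan), n = 80 and two-sided 0.05 give detectable slopes of 0.317 at 80% power and 0.367 at 90%, which round to the printed 0.32 and 0.37. On that assumption one slope is already a 90% figure and the other an 80% figure. This is only suggestive, since other SDs give other slopes. It does mean that the slopes cannot be called wrong, only uncheckable as printed.

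Finally, the practical weight is modest. The planned test is an interaction term in a repeated-measures model, the study is described as a pilot, and a null result should be read from its confidence interval. All of that stands, and the likeliest cause is 90% written for 80%. The statement still gives the wrong power for a primary question.

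**Conclusion.** The concern holds. At n = 80 and two-sided alpha 0.05, power to detect r = 0.307 is 79.5% to 81.3%, about ten points below the stated 90%, so the chance of a miss is about double what the plan implies. At 90% power the detectable correlation is 0.344 to 0.353.

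The conclusion rests on n = 80, which the plan states, and on a two-sided test, which is inferred. The alternatives tested change the size of the discrepancy, but none reproduces the printed pair of figures. The error affects how an age or BMI result will be read; it does not affect the number of subjects. It should be corrected, and confidence in the finding is high.

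**What to change.** In SA2, replace the correlation statement with one of these, for n = 80 and two-sided alpha 0.05:

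- 80% power to detect a correlation of 0.31; or
- 90% power to detect a correlation of 0.35.

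State sidedness and n in that sentence. Re-derive both slopes at the power chosen, and give for each its predictor, its outcome and the SDs assumed. If the p < 0.10 interaction threshold is meant to govern this power statement, say so and quote the power at that level (87% to 89% for r = 0.307 at n = 80).

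This costs a short recalculation and a change of wording. No subject, test or endpoint changes; the stated power, or the detectable correlation, simply becomes less favourable.

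### SA2 states 90% power for two unlabelled slopes, 0.32 and 0.37; as standardised slopes only 0.37 has it, and 0.32, like r = 0.307, has about 80%

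*Combined protocol and SAP*

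**What the plan says.** In section F (Data Analysis Plan), the paragraph on SA2 deals with BMI and age as continuous modifiers of the treatment effect. It says "we will have 90% power to detect a correlation coefficient of 0.307 or greater in the overall group in univariate analysis", and continues in the same sentence with "a slope of 0.32 for daily insulin dose or 0.37 for BMI in linear regression analysis". The 90% is the only power named there, so it governs all three figures.

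The other inputs are elsewhere in section F:

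- Under Power and Sample Size: "Desired α is set at 0.05".
- Under SA1, the overall group is 80 completers.
- Under SA1, the insulin-dose calculation proceeds "Assuming a SD of 18.8 to be conservative" (units/day), and the CGM-glucose calculation "assuming an SD of 10.03 mg/dl".
- The SA2 two-sample comparisons take their SDs from SA1.

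No SD of BMI or age appears in the documents. Section IV.A (Outcome Measures) lists the effect of age and BMI on response as the primary outcome for SA#2.

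**The concern.** Daily insulin dose is an outcome of this analysis and BMI is a predictor. The two slopes are therefore labelled by different kinds of variable, and neither has units. A reader cannot tell which regression each belongs to, or whether it is raw or standardised.

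The 90% also cannot apply to both as standardised slopes. At one sample size, alpha and power there is only one detectable standardised slope, so 0.32 and 0.37 cannot both be it.

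This sentence is the plan's only statement of sensitivity for BMI and age as continuous modifiers. Someone who takes 0.37 as units/day or mg/dl per kg/m2 would think the trial far more sensitive to a BMI gradient than it is likely to be, and could read too much into a null interaction.

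**Working it through.** **Inputs.** n = 80 and alpha = 0.05 (section F). Sidedness is not stated. Two-sided is taken because it reproduces the SA1 figures. SD of change: 18.8 units/day for insulin dose and 10.03 mg/dl for CGM glucose (SA1). SD of BMI: not given, so 4-7 kg/m2 is assumed where needed.

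**Check of conventions against SA1.** Detectable paired change = (1.960 + 0.842) x SD / sqrt(n).

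- Insulin dose, n=80: 2.802 x 18.8 / 8.944 = 5.9 units/day. With n=40: 8.3. Both match the plan.
- CGM glucose: 2.802 x 10.03 / 8.944 = 3.1 mg/dl. With n=40: 4.4. Both match.

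**Correlation.** Power = Phi(atanh(r) x sqrt(n-3) - 1.960). For r = 0.307: atanh(0.307) = 0.317; 0.317 x sqrt(77) = 2.78; 2.78 - 1.96 = 0.82; power = 79.5% (80.1% by simulation of the t test). The stated 90% does not reproduce. It would need r = 0.354, or n of about 108. A one-sided test gives 87%.

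**Standardised slope.** Let d = slope x SD(predictor) / residual SD. The test is a t test on 78 df with noncentrality d x sqrt(80).

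| d | Noncentrality | Power |
|---|---|---|
| 0.317 | 2.84 | 80% |
| 0.32 | 2.86 | 80.7% |
| 0.367 | 3.28 | 90% |
| 0.37 | 3.31 | 90.5% |

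The values detectable at 80% and 90% power round to the two printed figures. The correlation converts to the same scale as r / sqrt(1 - r^2) = 0.307 / sqrt(1 - 0.0942) = 0.323. So 0.307 and 0.32 are in effect one 80%-power result on two scales.

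**Raw slope of 0.37 per kg/m2.** Using the SA1 SD as the residual SD, the BMI SD needed for 90% power is 0.367 x SD(outcome) / 0.37:

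- Insulin dose: 0.367 x 18.8 / 0.37 = 18.6 kg/m2.
- CGM glucose: 0.367 x 10.03 / 0.37 = 9.9 kg/m2.

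Over the assumed BMI SDs, the power for 0.37 and the slope detectable at 90% power, 0.367 x SD(outcome) / SD(BMI), are:

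| Assumed BMI SD (kg/m2) | Insulin dose: power for 0.37 | Insulin dose: 90% slope (units/day per kg/m2) | CGM glucose: power for 0.37 | CGM glucose: 90% slope (mg/dl per kg/m2) |
|---|---|---|---|---|
| 4 | 10.7% | 1.72 | 26% | 0.92 |
| 5 | 14.0% | 1.38 | 37% | 0.74 |
| 6 | 18.1% | 1.15 | 50% | 0.61 |
| 7 | 23.0% | 0.99 | 63% | 0.53 |

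**Other insulin-dose SDs that SA1 mentions.** With 15 units/day, the low end of the centre's own range, power for 0.37 is 14-33% over BMI SD 4-7. With 7.6, from the metformin study, it is 41-85%. Neither reaches 90%.

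**The case against.** A reader might infer that the plan promises 90% power for a BMI slope and delivers only 11-23%. The documents do not support this as a flat statement. If the figures are standardised, 0.37 does have 90% power and the plan is right about it. The low range requires three things together: a raw slope, insulin dose as the outcome (the sentence attaches insulin dose to 0.32, not to 0.37), and an assumed BMI SD. With CGM glucose as outcome, or a smaller insulin-dose SD, power is higher.

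The standardised reading is itself an inference from a two-decimal match. The same pair appears whenever the outcome and predictor SDs are about equal. For example, with an insulin-dose SD of 15 and an assumed age SD of 14.8 years, the raw slopes per year of age are 0.317 x 15 / 14.8 = 0.32 at 80% power and 0.367 x 15 / 14.8 = 0.37 at 90%. This does not explain why 0.37 is labelled with BMI, but it shows that the origin cannot be settled from the text. It does not rescue the 90% on 0.32 either, because 0.32 is still the 80% value.

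The stakes are also limited. Power and Sample Size says that the overall sample size was set by the age subgroups, and calls the analyses by obesity level exploratory and not fully powered. The population section describes the BMI analysis as secondary. No sample size, test or decision rule rests on these slopes, and nowhere does the plan say that a null BMI result would exclude a given slope. Against that, section IV.A names "impact of age and BMI on response to therapy (SA#2") as a primary outcome, so its stated sensitivity should be correct.

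What stands is the missing labelling and a 90% that cannot apply to both slopes on the standardised reading.

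**Conclusion.** The clause is wrong as written, but the error is one of labelling and stated power, not of design.

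- **Provable from the plan's own n and alpha (two-sided):** r = 0.307 has about 80% power, not 90%. As standardised slopes, 0.32 and 0.37 cannot share one power: 0.32 has about 81% and 0.37 about 90%.
- **Likely but inferred:** the two figures are one standardised slope at 80% and at 90% power, printed with variable names that do not belong to them.
- **Conditional:** if 0.37 is a raw slope per kg/m2, the 90% fails with either SA1 planning SD at any BMI SD up to 7 kg/m2. Power is about 11-23% for insulin dose and 26-63% for CGM glucose at an assumed BMI SD of 4-7.

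The correlation and the 0.32 slope carry the same mislabelling in the same sentence and should be corrected together.

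**What to change.** Use one of two wordings.

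1. Keep the figures but label them as standardised slopes (slope x predictor SD / residual SD) for n=80 and two-sided 0.05: 0.32 at 80% power and 0.37 at 90%. Remove the attachments to insulin dose and BMI. State r = 0.307 at 80% power, or r = 0.354 at 90%.
2. Preferably, give raw-unit slopes for each predictor-outcome pair (BMI and age; insulin dose and CGM glucose) at one stated power, with the predictor SD and its source, and correct the power label on r = 0.307 as above. For example, at an assumed BMI SD of 5 kg/m2, the slopes are 1.38 units/day and 0.74 mg/dl per kg/m2 at 90% power (1.19 and 0.64 at 80%). For age, use 0.367 x SD(outcome) / SD(age) with the age SD stated.

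The cost is wording in the analysis plan only. Sample size, data collection and tests do not change. The stated sensitivity becomes less favourable.
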